questions. If they choose to participate after the initial contact, a written consent form will be mailed to them. This will allow the parents and/or legal guardians to discuss their participation with others before signing the written consent. 3) Research staff will attend the High Risk Follow-Up Clinic at CHLA. A licensed healthcare provider at CHLA, with the permission of the parent or legal guardian, will introduce the research staff to the family. The research staff will give more specific information about the study and answer any questions. If they choose to participate after the initial contact, a written consent form will be mailed to them. This will allow the parents and/or legal guardians to discuss their participation with others before signing the written consent. 4) A CHLA Clinical Research Coordinator (CRC) will coordinate with the High Risk Follow Up Clinic and potentially the NICU to review infants' medical records for eligibility and speak to families of potential participants. With the permission of the parent or legal guardian, the CRC will provide the research staff with the contact info. Research staff will call the parent or legal guardian and give more specific information about the study and answer any questions. If they choose to participate after the initial contact, a written consent form will be mailed to them. This will allow the parents and/or legal guardians to discuss their participation with others before signing the written consent.

Inclusion Criteria. Infants will be 3-6 months of adjusted age at the first visit, +/- 30 days. Infants will be defined as at risk in accordance with the definition below (confirmed by the PI or the CHLA CRC) ¹⁵:

CCS HRIF PROGRAM MEDICAL ELIGIBILITY CRITERIA

UPDATED 01/2017

Data should be collected on infants/children under three years of age who meet California Children's Services (CCS) HRIF medical eligibility criteria **and** who met CCS medical eligibility criteria for Neonatal Intensive Care Unit (NICU) care **OR** had a CCS eligible medical condition at some time during their stay in a CCS-approved NICU, even if they were never a CCS client. **Infants are medically eligible for the HRIF Program when the infant:**

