Data Collection. All infants will be assessed in their homes once per month (+ or - 5 days), from 3-6 months of corrected age until sitting onset (can maintain independent sitting > 30 s) or 9 months corrected age, whichever occurs first. We have chosen this as our intervention endpoint because 1) once sitting is established, the way in which infants use their legs shifts drastically (from mostly supine and some prone free movement to primary use as postural stability) and 2) if they are not sitting independently by 9 months corrected age it is straightforward clinically to identify significantly delay. The goal of our intervention is to get them on the "right track" early, not to provide intervention once a significant delay has occurred. We have chosen to start our intervention at 3 months of corrected age, as this is just before relationships have been observed between leg movement frequency and later functional outcomes (as described in the significance section). Sensor Data. To record leg movement rate, infants will wear custom leg warmers with a pocket that securely holds a movement sensor at each ankle from the morning visit until bedtime. The caregivers will remove the leg warmers and sensors when they put their infant to bed for the night (~10-12 hours later). We will return to pick them up the next day. Amount and type of leg movements will be determined using our existing, validated software algorithms. Assessments. We will measure the infant's weight, length, head circumference, thigh and shank lengths and circumferences. We will document medical and therapy interventions being received and assess motor skills using the Alberta Infant Motor Scale (AIMS), a standardized, norm-referenced observational scale¹⁶. We will record 5 minutes of spontaneous movement video to have a visual reference for data. We will record the caregiver teaching the child a novel task and assess the caregiver-infant interaction using the Nursing Child Assessment Teaching Scale (NCAT), a evidence based standardized-assessment tool¹⁷.

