producing alternating kicks while smiling and singing for 10 total alternating kicks (5 each leg) and then encouraging the baby to perform alternating kicks (not assisting) for 15 seconds and responding with singing and smiling if he or she does. Five sets will be performed each diaper change. Fidelity. Caregivers will keep logbooks of the amount and type of movement experience they provide. This will assist our efforts to create a manual of intervention strategies for future grant proposals. Despite best intentions, however, logbooks are often incomplete; the GAME study reported ~ 50% completion¹⁹. Our main fidelity measure in this study will be the movement rate and proportion of unilateral movements demonstrated by the infants across days and months. We will be able to compare these data to our existing observational data to measure the intervention effect size.

Follow Up: Families will be contacted by email or phone every 3-4 months from after the last visit until 24 months of corrected age for updates on their child's medical and developmental status.

Statistical test and analyses were performed using SPSS (Version 24; IBM, Corporation, Armonk, NY, USA). We first checked all variables for normality by plotting histograms and visually inspecting the data. Given the sample size and visual inspection of the variables, we chose to analyze our data using non-parametric statistics. The median and range were used to represent all descriptive statistics for the first and last visit. Wilcoxon Signed Ranked tests ($\alpha = 0.05$) were used to compare the leg movement rates, adherence, and NCAST-Teaching total score to test for significant differences between the first and last visits. Spearman rank order correlations ($\alpha = 0.05$) were used to test for significant relationships between quality of caregiver-child interaction and adherence to the intervention and leg movement rate at all visits.

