Sample size justification. We determined our sample size of 12 for this pilot intervention study based on our observational pilot data. In our pilot data, we found large effect sizes (Cohen's $d = 0.8 - 1.3$) for leg movement quantity (movements per hour of awake time) between 12 infants with TD and 24 infants AR (anticipate ~12 good and ~12 poor neuromotor outcomes). With the planned primary comparison of leg movement of those who received intervention ($N = 12$) versus those who did not ($N = 24$), we should be able to detect an effect of Cohen's d of 1.0 at 9 months, with $\alpha = 0.05$ and 80% power.

Potential Risks

Wearable Sensors: There is a small risk of skin irritation from wearing the legwarmers all day. Parents will be able to visually see their infants' feet at all times (they are not covered) and can remove the legwarmers briefly as desired to inspect their infant's skin. Although the movement sensors are small, they are not small enough to present a choking hazard. They measure 1.4 inches by 1.9 inches, larger than the standard choking hazard guidelines.²⁰

Storage of Materials. There is a small risk of disclosure of participant's personal information. Data collected from participants includes biological data of leg movement activity, video recordings and health status information. All information collected will be kept private and secure. Password protection and secure internal computer networks and REDCap, a HIPAA-compliant database system hosted by USC, will be used to collect and store data. Hard copies of data, including 2 backup copies on external hard drives, will be stored in a locked, waterproof, fireproof safe in a locked room in a secured building (keys, identification cards) on a secured campus (identification cards, security patrol). Unique identifier codes will be used to separate all data collected from any personal identifying information. Laboratory members will have access to data identified by code for analysis and manuscript preparation, while only the PI and Research Assistant (RA) will have access to identifying information for participant tracking purposes.

Intervention. As is typical with trying to get an infant to perform any desired behavior, there is a risk that

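### The Spearman correlations of interaction quality, adherence and leg movement rate take no account of corrected age, although infants up to 3 months apart (about 5 at the limits) can share an early visit number

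*Combined protocol and SAP*

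**What the plan says.** The statistical paragraph at the end of the Approach section states that Spearman rank correlations, tested at the 0.05 level, "were used to test for significant relationships between quality of caregiver-child interaction and adherence to the intervention and leg movement rate at all visits". It names no covariate, stratification or partial correlation, and no age adjustment appears elsewhere in the document. It does not say whether the correlations are run visit by visit or on all visits pooled.

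On age, Inclusion Criteria states: "Infants will be 3-6 months of adjusted age at the first visit, +/- 30 days". Data Collection states: "All infants will be assessed in their homes once per month (+ or - 5 days), from 3-6 months of corrected age until sitting onset", with the end of visits at sitting "or 9 months corrected age, whichever occurs first". Visit number is therefore counted from each infant's own entry, not from a common age.

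Two other statements bear on whether the measures move with development. Data Collection justifies the end of visits by saying that "once sitting is established, the way in which infants use their legs shifts drastically". The statistical paragraph also plans Wilcoxon tests that "were used to compare the leg movement rates, adherence, and NCAST-Teaching total score to test for significant differences between the first and last visits".

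**The concern.** A correlation between two measures can come from a third variable that drives both. Age is an obvious candidate in infants between about 2 and 9 months of corrected age. If older infants move their legs at a different rate, and their caregivers also score differently on the teaching scale or adhere differently, the plain Spearman coefficient picks up the shared age trend. This is confounding: it would occur with only one value per infant, and a larger sample would not remove it.

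The reading of the result is at stake. A significant coefficient would be taken to mean that better interaction or adherence goes with more infant movement, which is the idea behind a caregiver-provided intervention. It might mean only that infants of different ages differ on both measures.

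**Working it through.** **The plan's own figure.** The only stated design figure is 80% power for the comparison of 12 treated with 24 untreated infants at d = 1.0 and alpha 0.05 (Sample size justification). It reproduces as a two-sided calculation: 1/√(1/12 + 1/24) = 2.828, and Φ(2.828 - 1.960) = 80.7%; the noncentral t with 34 df gives 78.5%. It does not concern the correlations, for which the plan gives no figure.

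**Age spread at a shared visit number.** Taking 30 days as one month, entry runs from 3 - 1 = 2 to 6 + 1 = 7 months at the limits. At visit k the youngest possible age is 2 + (k - 1) and the oldest is the smaller of 7 + (k - 1) and 9.

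| Visit | Youngest-oldest (months) | Maximum spread |
|---|---|---|
| 1 | 2-7 | 5 |
| 2 | 3-8 | 5 |
| 3 | 4-9 | 5 |
| 4 | 5-9 | 4 |
| 5 | 6-9 | 3 |
| 6 | 7-9 | 2 |
| 7 | 8-9 | 1 |

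Without the tolerance, entry at 3-6 months gives a spread of 3 months at the early visits. Sitting before 9 months narrows the later rows further.

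**Size of the effect at one visit.** Inputs: n = 12 (Sample size justification) and alpha 0.05 (statistical paragraph). The correlations of each measure with age, a and b, are assumptions, because the documents give none. With no direct link, x = a·age + √(1 - a²)·noise and y = b·age + √(1 - b²)·noise, so their underlying correlation is ab. For normal variables the expected sample Spearman coefficient is 6/[π(n + 1)] × [asin(ab) + (n - 2)·asin(ab/2)]. For a = b = 0.5 this is 0.1469 × (0.2527 + 10 × 0.1253) = 0.22. The false-positive rates below are simulated.

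| a = b | ab | Expected rho | False positives, plain Spearman |
|---|---|---|---|
| 0 | 0 | 0 | 5.2% |
| 0.3 | 0.09 | 0.08 | 5.9% |
| 0.5 | 0.25 | 0.22 | 11.4% |
| 0.6 | 0.36 | 0.32 | 18.3% |
| 0.7 | 0.49 | 0.44 | 33.5% |

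Repeat runs with normal or uniform age agree closely for the first three rows. They range over about 18-20% at 0.6 and 33-36% at 0.7. Opposite trends (0.5 and -0.5) give a spurious negative correlation of the same size.

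**One weak trend.** With a/b of 0.5/0 the rate is 5.1%. With 0.5/0.1, 0.5/0.2 and 0.7/0.2 it is about 5.5% to 7.4%. Inflation needs a moderate to strong trend in both measures.

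**After adjustment.** The partial Spearman correlation is (r_xy - r_xa·r_ya)/√[(1 - r_xa²)(1 - r_ya²)], tested on n - 3 = 9 df. In every row with a trend in both measures, it brings the rate back to 5.3-5.8%.

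**If visits are pooled.** This used 12 infants, about 40 rows and assumed sitting ages. With a = b = 0.5 and no within-infant correlation, the plain rate is 33.8% and the age-adjusted rate 5.6%. With a within-infant correlation of 0.5 the figures are 39.8% and 11.8%. That correlation alone, without any age trend, gives about 11%. Age adjustment therefore does not repair a pooled analysis.

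**Price of adjusting.** The critical |rho| is t/√(df + t²). With 10 df it is 2.228/√(10 + 4.964) = 0.576; with 9 df, 2.262/√(9 + 5.117) = 0.602.

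**The case against.** The strongest reply is that the premise is missing. Bias needs both measures in a pair to vary with age, and nothing in the documents shows that the teaching-scale score or adherence does. A reader might infer it from the planned first-versus-last tests, but planning a test for change is not evidence of change. Change since entry is also not the same as a difference between older and younger infants at one visit number. For leg movement, the plan applies a single threshold of 1200 movements per awake hour from 3 months to sitting, and places the drastic shift in leg use after sitting, where visits stop. This stands: the documents do not support saying that the correlations will be spurious, nor the upper end of the assumed range in particular. They do not exclude age trends either, and the planned test gives no protection if these exist.

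A reader might also infer that a 5-month spread applies at every visit. It does not: it requires both tolerance extremes, and it shrinks after visit 3. Nor need 12 infants remain at later visits; with 6, the rate at 0.5/0.5 is about 8.0%.

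Finally, one might want the plain correlations dropped altogether. That goes too far. Within an infant, age rises in step with time on the intervention, so adjusting pooled rows for current age could remove change that adherence itself produced.

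That this is a small pilot with a different primary comparison limits how much the point matters. It does not answer it, because a declared significance test invites a conclusion.

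**Conclusion.** The point holds as a conditional one. The correlations are unadjusted, and infants 3 months apart, or about 5 at the tolerance limits, can share an early visit number. If both measures in a pair vary with age, a correlation can arise without a direct link. With 12 infants at one visit, the false-positive rate is about 6%, 11%, 18% and 33% at age correlations of 0.3, 0.5, 0.6 and 0.7 in both measures, and close to 5-7% if either trend is weak. These age correlations are assumptions, so the actual size of the bias is unknown.

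A reader might infer that the pilot's main result is compromised. The documents do not support that: the primary comparison in Sample size justification is a different one, and its power is unchanged. What is affected is the interpretation of the correlations. The remedy is cheap enough to be worth making.

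**What to change.** State that the correlations are run separately at each visit, with the number of infants at each. At one visit number all infants have nearly the same time since entry, so adjusting for age there does not remove time on the intervention. Beside each plain Spearman coefficient, report the partial Spearman correlation controlling for corrected age at that visit. Base any claim of a relationship on the adjusted result, and label it exploratory.

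If visits are to be pooled, use a model with an infant effect, corrected age at entry, and time since entry as a separate term. Age adjustment alone does not correct for repeated rows from the same infant.

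No new data are needed, because corrected age is already used for eligibility and for the end of visits. The statistical paragraph is in the past tense; if the analysis has been done, the adjusted coefficients can be added from the existing data. The cost is one degree of freedom: 9 instead of 10 with 12 infants, so that the critical |rho| is 0.602 instead of 0.576. It is larger where fewer infants remain: with 8, 0.754 instead of 0.707.

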Intervention. At each visit, the caregiver will be reminded of the infant's movement. The research team will spend 15 minutes interacting with the caregiver to determine possible ways to achieve the goal of 1200 movements per hour of awake time, with a variety of movements. Strategies to increase leg movements will be encouraged based on the infant's developmental level and what they demonstrate a response to, including: shake a toy when infant moves legs, sing a line of a song when infant moves legs, change the position of the infant to encourage more leg movement, or lightly tickle the legs and feet of the infant. The intervention will use the GAME (Goals - Activity - Motor Enrichment) protocol, a motor learning, environmental enrichment intervention that has recently been shown to be effective for improving motor skills in infants at high risk of cerebral palsy compared to standard care. The intervention is based on the principles of active motor learning, family centred care, parent coaching and environmental enrichment. Intervention was customised to parent goals and enrichment style and the child's motor ability. To increase the dose of motor practice families were provided with a home program containing suggested activities according to identified goals^{14,18,19}. We are expanding this effective intervention by applying it to a new population (infants broadly at risk as opposed to specifically at risk for cerebral palsy) and by specifically quantifying the dose of leg movement experience (amount and type). Otherwise, all intervention will be consistent with the established, published protocol. A customized logbook of all exercises with demonstration pictures of the baby, instructions, and tracking (amount and type) will be provided to the family each visit. Example Intervention Strategy. The research team and family determine that the baby likes Mom smiling and singing "You are my sunshine". They decide that every time the baby's diaper is changed, Mom will demonstrate by assisting the baby with

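### The Spearman correlations over all visits have no stated unit of analysis; if infant-visits are pooled, the 5% test level fails when both variables cluster within infant

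*Combined protocol and SAP*

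**What the plan says.** The statistical paragraph (end of the Approach section, after Follow Up) describes two sets of tests, each at alpha 0.05.

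- Wilcoxon signed-rank tests compare leg movement rate, adherence and the NCAST-Teaching score, "to test for significant differences between the first and last visits". Each infant gives one pair of values.
- Spearman rank correlations are used "to test for significant relationships between quality of caregiver-child interaction and adherence to the intervention and leg movement rate at all visits". This set extends to every visit.

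The design makes these visits repeated and unequal in number. Data Collection sets a monthly visit for each of 12 infants "until sitting onset (can maintain independent sitting > 30 s) or 9 months corrected age, whichever occurs first". Under Inclusion Criteria, "Infants will be 3-6 months of adjusted age at the first visit, +/- 30 days". An infant who enters early or sits late therefore gives more visits than one who enters late or sits early.

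The documents give no method for repeated measures, no multiplicity rule and no statement that the correlations are exploratory. It is also unclear whether two pairs are meant (interaction with adherence, interaction with rate) or three.

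The sample size section names a different primary analysis: "With the planned primary comparison of leg movement of those who received intervention" with those who did not (12 versus 24).

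**The concern.** The usual Spearman p-value assumes independent pairs of observations. Repeated visits from one infant are not independent if infants differ consistently in both variables. Pooling them then counts the same between-infant information several times and gives more weight to infants with more visits.

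These are the plan's only tests of whether caregiver-child interaction goes with adherence or with leg movement. The Fidelity paragraph says the caregiver logbooks will feed a manual of strategies for future grant proposals, so a spurious association could be carried forward.

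**Working it through.** **1. The stated figure.** The only figure given for these tests is alpha 0.05; two-sided is assumed. A single Spearman test on 12 independent infants has a simulated error of 5.3%, so the test itself is sound at this size. The 80% power in the sample size section belongs to the 12-versus-24 comparison. It reproduces (0.807 by normal approximation, 0.785 by noncentral t) and has no bearing here.

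**2. Number of visits.** From the documents: 12 infants, monthly visits, entry at 3-6 months, end at sitting or 9 months. Assumed, because no distribution is given: entry uniform over 3-6 months and exit uniform over 6-9 months. The span from entry to exit is then triangular on 0-6 months. The probability that it reaches 1, 2, 3, 4 or 5 months is 17/18, 14/18, 9/18, 4/18 or 1/18. Expected infants at visits 1 to 6 are 12, 11.3, 9.3, 6.0, 2.7 and 0.7. They sum to 42 points, or 3.5 visits per infant.

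**3. Visits pooled.** With no true association, clustering multiplies the variance of the pooled correlation by about

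1 + (m_w − 1) × ICC_x × ICC_y, where m_w = Σm²/Σm and m is an infant's number of visits.

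Under the scheme in step 2, the mean of m² is (1×1 + 4×3 + 9×5 + 16×5 + 25×3 + 36×1)/18 = 249/18 = 13.83. So m_w = 13.83/3.5 = 3.95. The approximate error is P(|Z| > 1.96/√inflation). The last column is from 20,000 simulated trials per row.

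| ICC in both variables | Inflation | Approximate error | Simulated error |
|---|---|---|---|
| 0 | 1.00 | 5.0% | 4.9% |
| 0.3 | 1.27 | 8.2% | 7.5% |
| 0.5 | 1.74 | 13.7% | 12.7% |
| 0.7 | 2.45 | 21.0% | 19.7% |

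The product of the two ICCs drives the result. Simulated error is 11.4% for ICCs of 0.7 and 0.3, 7.2% for 0.7 and 0.1, and 4.9% for 0.7 and 0.

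Sensitivity, at ICC 0.3 / 0.5 / 0.7:
- at least two visits per infant: 7.9 / 12.4 / 20.0%;
- entry spread over 2-7 months (the 30-day allowance): 7.6 / 13.0 / 21.4%;
- seven visits for every infant, the nominal maximum for entry at 3 months: 11.0 / 19.9 / 31.3%;
- half of the adherence values missing at random by visit (about 21 points): about 6 / 9 / 12%;
- half of the infants with no adherence data at all: about 7 / 12 / 19%, with about 6 infants left.

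**4. Each visit tested separately.** Suppose a test is run wherever at least 6 infants remain. Two pairs give about 7 tests, each with an error of 5.2-5.5%. The chance of at least one p < 0.05 is 31-34% over ICC 0 to 0.7. Three pairs give about 11 tests and 43-46%. As a check, 8 independent tests give 1 − 0.95⁸ = 33.7%.

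**5. One mean per infant.** Simulated error is 5.0-5.7% over ICC 0 to 0.7.

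**6. Precision.** The critical |ρ| is t/√(n − 2 + t²). At n = 12 it is 2.228/√(10 + 4.964) = 0.58. At 42 points treated as independent it is 2.021/√(40 + 4.085) = 0.30.

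**The case against.** A reader might infer that the stated 5% level is lost however the tests are run. The documents do not support that. The only level stated is per test, and visit-by-visit testing keeps it. What rises is the chance of at least one false positive across the set, which the plan never undertakes to control. One summary per infant is a third possible reading, and it is valid as it stands. This part of the objection stands in full: the defect is an unspecified unit of analysis, and the level fails only under pooling.

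The size under pooling also rests on assumptions. The documents give no ICC, visit count or sitting-age distribution. The Fidelity paragraph expects incomplete logbooks and cites about 50% completion in an earlier study. Scattered gaps would lower the inflation for the adherence pair, as step 3 shows, but gaps by whole infant would hardly change it. This too stands, and it is why the result is given as a range. It also means that n = 12 is not assured for adherence under any method.

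Finally, this is a 12-infant pilot and the correlations are secondary. That limits the consequences, but it does not make pooled p-values valid, and the remedy is small.

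**Conclusion.** The concern holds for pooled visits. The per-test 5% level then fails whenever both variables cluster within infant: about 8 / 13 / 20% at an assumed ICC of 0.3 / 0.5 / 0.7 with about 42 points. There is no excess if either ICC is 0, and the excess is smaller for adherence if logbook entries are missing at random. For visit-by-visit tests, the 31-34% across about 7 tests calls for an exploratory label and does not show that the stated level is wrong.

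A reader might extend the point to the trial's main results. The documents do not support this: neither the 12-versus-24 primary comparison nor the first-versus-last Wilcoxon tests use these correlations. The figures assume normal variables, the entry and exit scheme in step 2, and p-values from the t approximation.

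**What to change.** Make the infant the unit of analysis.

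- Name the pairs (two or three). Run one Spearman correlation per pair on one summary per infant, for example the mean over available visits.
- If visits are to be pooled, take the p-value and interval from resampling or permuting whole infants.
- Report the number of infants and visits behind each value. Expect fewer than 12 infants for adherence.
- Label these correlations, and any per-visit ones, exploratory, and give the number of tests.

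A repeat adjusted for mean corrected age, or one without the first visit, is optional. Coaching takes place at every visit, so every rate is recorded on a coaching day and the first visit is not special in that respect.

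The cost is a short paragraph, plus a small reanalysis if the tests have been run (the statistical paragraph is in the past tense). Apparent precision falls: the critical |ρ| is 0.58 at n = 12 against 0.30 for 42 pooled points. Power at n = 12 is about 34% for a true correlation of 0.5 and 69% for 0.7. A summary per infant describes differences between infants and does not show change within an infant.

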ClinicalTrials.gov Identifier: NCT03082313

Date uploaded 10/20/21

Version 02/10/18

Leg Movement Rate before and after a Caregiver- Provided Intervention for Infants at Risk of Developmental Disability: A Pilot Study

Protocol: Intervention: Leg Movement Rate

Significance

Infants with developmental delay often experience lifelong functional limitations in motor, cognitive and social domains. A strictly-defined, conservative estimate recently determined that ~9% of infants in the US are eligible for early intervention services because they are at risk for developmental delay. Diagnoses of developmental delay are typically made at 18 to 24 months of age¹ and current practice is to provide infrequent, low intensity therapies or no intervention across infancy²⁻⁴. In infants born preterm, for example, low intensity developmental interventions have generally demonstrated short-term benefits that are not sustained into the school years⁵⁻⁸. Basic science evidence supports that early and intense therapy intervention is more effective at promoting optimal neuromotor structure and function⁹⁻¹¹. Given this information, dosing of pediatric physical therapy intervention is a current topic of high interest in the field¹², and researchers are starting to investigate the feasibility of different approaches for providing early, intense interventions^{13,14}. Although these approaches are laudable and strongly theoretically based there is a fundamental gap: we do not know what amount and type of movement experience is necessary and sufficient to have a positive effect on the development of infant neuromotor control. This proposal will address this fundamental question by increasing the leg movement experience of infants at risk for developmental delay to an evidence-based minimum threshold for quantity and type of movement and measuring the association between amount of leg movement experience and motor development rate.

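### The 80% power belongs to a primary comparison (12 treated versus 24 untreated infants at 9 months) that the statistical paragraph does not specify, and it does not carry over to the tests listed there

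*Combined protocol and SAP*

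**What the plan says.** The Sample size justification is the only place that calls any analysis primary: "With the planned primary comparison of leg movement of those who received intervention" (N = 12) versus those who did not receive it (N = 24). It states that an effect of Cohen's "d of 1.0 at 9 months" should be detectable with alpha 0.05 and 80% power. It attributes the choice of 12 to observational pilot data, in which 12 typically developing and 24 at-risk infants differed by d = 0.8 to 1.3.

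The statistical paragraph at the end of the Approach section says that Wilcoxon signed-rank tests "were used to compare the leg movement rates, adherence, and NCAST-Teaching total score to test for significant differences between the first and last visits", and adds Spearman correlations. It names no two-sample test, comparator cohort or 9-month time point. On method it says "we chose to analyze our data using non-parametric statistics". It is in the past tense: "Statistical test and analyses were performed using SPSS".

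The Fidelity text, just before it, says "We will be able to compare these data to our existing observational data to measure the intervention effect size".

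Under Recruitment, 12 at-risk infants are enrolled and no concurrent control group is described. Under Inclusion Criteria, the first visit is at 3 to 6 months adjusted age, plus or minus 30 days. Under Data Collection, monthly visits end at sitting onset or at 9 months corrected age, whichever is earlier. Later follow-up is by email or phone.

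**The concern.** An analyst who works from the statistical paragraph will not find the comparison that the protocol calls primary and for which it claims power. A reader of the public record could credit the 80% to the first-versus-last test, because that is the only test of change listed.

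That test cannot take the place of the missing one. Every infant is older at the last visit than at the first, and no untreated infant enters the test. Ending visits at sitting onset removes one source of developmental change, the shift in leg use that the protocol describes, but not ageing before sitting.

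The 9-month comparison has a gap of its own. An infant who sits before 9 months has no planned sensor recording at 9 months. If only infants seen at that age were analysed, the treated group would be selected on motor outcome. The documents give no rule for this.

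**Working it through.** **1. Reproduce the stated power.** Inputs from the Sample size justification: n1 = 12, n2 = 24, d = 1.0, alpha = 0.05. Sidedness is not stated; two-sided is assumed.

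- Normal approximation: d × √(n1·n2/(n1+n2)) = 1.0 × √(288/36) = √8 = 2.828. Power = Φ(2.828 − 1.960) = Φ(0.868) = 0.807. The d detectable with 80% power is (1.960 + 0.842)/2.828 = 0.99.
- Noncentral t, 34 degrees of freedom: 0.785 (d for 80% power: 1.02).
- Mann-Whitney, normal data, 200,000 simulations: 0.759.
- One-sided versions give 0.882 (normal) and 0.870 (t), which do not match 80%.

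The stated figure is therefore a two-sided, two-group calculation with all 36 infants contributing a value.

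**2. Does the 80% apply to the listed test?** The signed-rank test depends on the mean change divided by the SD of the within-infant difference (dz). With n = 12, the exact test at two-sided 0.05 and normal differences (400,000 simulations), power is 0.799 at dz = 0.935 and 0.804 at dz = 0.94. So 80% power needs about 0.94 SD of the difference.

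The documents give neither that SD nor the correlation between first and last visit. If the mean change is 1.0 between-infant SD, then dz = 1.0/√(2(1 − ρ)):

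| Assumed ρ | dz | Signed-rank power |
|---|---|---|
| 0 | 0.707 | 0.559 |
| 0.3 | 0.845 | 0.715 |
| 0.5 | 1.000 | 0.851 |
| 0.7 | 1.291 | 0.972 |

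Power runs from 56% to 97% on a quantity the plan does not state, so the 80% cannot be attached to this test.

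**3. Ageing between the compared visits.** Earliest entry is about 2 months (3 months minus 30 days), and 9 − 2 = about 7 months to the latest possible last visit. Latest entry is about 7 months (6 months plus 30 days), and 9 − 7 = about 2 months, less if sitting comes sooner. To show what ageing alone could do, assume no intervention effect and an age drift of 0, 0.3, 0.5 or 0.8 SD of the difference. The signed-rank test then rejects in 4.2%, 13.8%, 31.5% or 66.7% of trials. The drifts are assumed, and their direction is not given either.

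**4. Missing 9-month values.** If 9 or 6 treated infants have a value at 9 months and all 24 comparators are kept (both assumed):

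- 9 versus 24: √(216/33) = 2.558; Φ(2.558 − 1.960) = 0.725 (t 0.698, Mann-Whitney 0.665).
- 6 versus 24: √(144/30) = 2.191; Φ(2.191 − 1.960) = 0.591 (t 0.562, Mann-Whitney 0.507).

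The ages at which the comparators were measured are not given, so losses on that side are unknown.

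**The case against.** The best defence is that the document, read as a whole, does foresee the comparison. The Sample size justification gives groups, outcome, age, alpha and power, and the Fidelity text reserves the phrase intervention effect size for the comparison with observational data. This stands against a reading that a reader might form, namely that the between-group comparison would never be run. The documents do not support that. What they lack is the test, the comparator's definition and ages, and a rule for infants without a 9-month value.

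A reader might also infer that the document names rival primary analyses, since the title says "Leg Movement Rate before and after a" and the Significance section aims to measure the "association between amount of leg movement experience and motor development rate". Neither is called primary. There is one explicit designation and one omission.

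Nor does the statistical paragraph call the first-versus-last difference an intervention effect. The ageing point is thus a caution on interpretation and a reason why that test cannot fill the gap. It does not refute a causal claim in that paragraph.

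Two further points are fair. The choice of 12 is credited first to the pilot data, so it is the power statement, more than the number itself, that hangs on the missing test. And the figures under assumed correlation, drift and attrition show sensitivity only. That this is a pilot would excuse a purely descriptive plan, but this plan claims 80% power for a primary comparison and tests at 0.05.

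**Conclusion.** The point holds as an inconsistency that must be reconciled. The only analysis designated primary, and the one to which the 80% power belongs, is absent from the statistical paragraph and is not specified well enough elsewhere to be run as planned.

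It would be wrong to conclude that the power was miscalculated. The 80% reproduces to within about 2 points by normal approximation or t test, and is about 76% for a rank test, provided all 36 infants have a 9-month value and the data are near normal. The error lies in where the figure can be applied: it does not describe the signed-rank test, which needs about 0.94 SD of the difference with 12 infants.

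First-versus-last change spans up to about 7 months of ageing and cannot serve as the estimate of the intervention effect in either direction. A 9-month analysis limited to infants seen at that age would select on motor outcome. That the 24 untreated infants are the at-risk pilot cohort is inferred from the matching number and is not stated.

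**What to change.** **Preferred.** Add the 12 versus 24 comparison to the statistical paragraph as the primary analysis, and state:

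- the comparator cohort (apparently the 24 at-risk pilot infants);
- a two-sample test; a rank-based one matches the plan's non-parametric choice;
- one corrected age common to both groups;
- how infants without a value at that age are handled, and how many per group contribute.

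Attach the power statement to this test only. Label the comparison external and non-randomised. If it is added after the analysis, as the past tense suggests it may be, mark it as not pre-specified in the analysis section.

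**Fallback, if comparator data at a common age do not exist.** Withdraw the 80% power claim and the designation of the between-group comparison as primary. Record this as a dated change of primary analysis, made after the analysis if that is so. Justify 12 infants on pilot or feasibility grounds, and report first versus last visit as descriptive. This is more than a wording change, because it removes the only stated primary analysis and the power basis.

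**In either case,** report first versus last as within-infant change that includes ageing, not as an intervention effect.

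**Cost.** The preferred route needs revised text, a check of the ages at which the comparators were measured, and one analysis on data the protocol calls existing. It remains open to confounding and may lose infants to age alignment. The fallback needs text and disclosure only, but gives up the between-group claim.
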